We will conduct a cluster randomized trial of an informative intervention targeting the over-prescription of scheduled drugs with patient death as the unit of randomization.

The follow outcomes will be analyzed:

- 1) Fewer opioid prescriptions written among clinicians receiving the letter, compared to controls;
- 2) Lower cumulative Morphine Equivalent Dose (cMED) among clinicians receiving the letter (as indicated by dosing on prescriptions filled);
- 3) More frequent use of CURES among clinicians receiving a letter;
- 4) Fewer opioid prescriptions for ≥ 100 milligram morphine equivalent (MME)
- 5) Fewer benzodiazepine co-prescriptions

In the main analysis, we will compare a 12-month baseline period to a 12-month post-treatment follow-up period.

Interventions and Duration

The intervention will be a one-time treatment for all participants, with a three-month and a one year follow-up period to measure the persistence of the effects after the intervention.

The following intervention will be analyzed:

A courtesy communication informing prescribers of the death of a former patient where prescription drug overdose was the primary cause or contributed to the cause of the death. The letter will invite prescribers to review materials regarding the clinical guidelines from the Center of Disease Control, the California Department of Public Health, and the San Diego County Prescription Drug Abuse Medical Task Force for a more prudent prescription of those drugs.

Sample Size and Population

Our sample will consist of a heterogeneous group of clinicians and allied health professionals with scheduled drug prescribing privileges practicing in San Diego County who prescribed a Schedule II-IV drug (i.e., drugs as defined by the United States Controlled Substances Act as having an abuse potential, but also a currently accepted medical use) to a person who died as a result of a Schedule II-IV accidental drug death.

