1.2 Secondary Objectives

Our secondary objective is to observe frequency of CURES use and the number of "new starts".

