3. STUDY DESIGN

The trial is a cluster-randomized controlled trial with prescriber as the unit of randomization. The primary aim is to test the ability of the informative intervention to reduce the number of Scheduled drug prescriptions. We will randomize prescribers in a 1:1 design where half will be in the control group while the other half receives the intervention. All physicians involved in prescription drug over-dosage related deaths in the 12-month baseline period will be randomized to receive a letter regarding that death as well as guidelines for future consideration regarding prescribing practices. The intervention will be followed by a one year follow-up period to measure persistence of effects. Data from the Controlled Substance Utilization Review and Evaluation System 2.0, which is California's prescription drug monitoring program, will be extracted and transferred to the Data Coordinating Center on a weekly basis.

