5. STUDY INTERVENTIONS

5.1 Interventions, Administration, and Duration

A letter signed by the Chief Deputy Medical Examiner of San Diego County will notify prescribers of the death in their practice. The letter will outline the annual number and types of prescription drug deaths seen by the medical examiner, discussed the value of and way to access the State's prescription drug monitoring program, and discussed five CDC guideline-recommended safe prescribing strategies: 1) Avoid co-prescribing of opioids with benzodiazepines, 2) prescribe minimal dose necessary for acute pain, 3) consider slow tapers with pauses to below 50 MME per day, 4) avoid prescriptions lasting greater than 3-months for

pain, and 5) prescribe naloxone in conjunction with opioids for patients taking ≥ 50 MME per day.

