9.4.2 Secondary outcomes

As secondary hypotheses, we evaluate if the intervention cohort had 1) fewer high-dose opioid prescriptions (≥ 50 or > 90 MME per day), or 2) fewer new patients who were started on opioids. High-dose prescriptions were evaluated using censored regression on percent of clinician fills on high-dose. Chance of a fill being a “new start” were evaluated using logistic regression. These analyses were also conducted within a difference-in-differences framework.

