post-intervention beginning one month after the letter was sent to washout contamination by prescriptions written before receipt of the letter but filled afterwards. For the one-year analysis we will include a regressor to control for the 3-month effect. We will perform sensitivity analysis on regression assumptions. As secondary hypotheses, we evaluate if the intervention cohort had 1) fewer high-dose opioid prescriptions (≥ 50 or > 90 MME per day), or 2) fewer new patients who were started on opioids. High-dose prescriptions will be evaluated using censored regression on percent of clinician fills on high-dose. Chance of a fill being a “new start” will be evaluated using logistic regression. These analyses will also be conducted within a difference-in-differences framework.

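### Fewer new starts is a hypothesis about a number of patients but is tested as a share of fills, which can miss or reverse a fall; the high-dose test has the same gap in a weaker form

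*Combined protocol and SAP*

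**What the plan says.** Section 9.4.2 (Secondary outcomes) sets two secondary hypotheses, and Section 9.5 repeats them. The first is that the letter cohort would have a smaller number of high-dose opioid prescriptions. The second is that it would have "fewer new patients who were started on opioids". Section 1.2 also speaks of a number: "Our secondary objective is to observe frequency of CURES use and the number of" new starts.

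The models named in Section 9.5 are for other quantities. For high-dose prescribing: "High-dose prescriptions will be evaluated using censored regression on percent of clinician fills on high-dose". For new starts: "Chance of a fill being a “new start” will be evaluated using logistic regression". Both sit in a difference-in-differences framework. No count model, rate, offset or per-clinician number is given for either.

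Elsewhere the plan expects volume to fall. The first outcome listed in the Précis (Design and Outcomes) is "Fewer opioid prescriptions written among clinicians receiving the letter, compared to controls", and Section 3 states: "The primary aim is to test the ability of the informative intervention to reduce the number of Scheduled drug prescriptions". The Précis also lists a count-worded outcome for prescriptions of at least 100 MME. Section 9.5 gives no model for either of these two Précis outcomes.

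**The concern.** A share of fills has total fills as its denominator, and the letter is intended to change total fills after randomisation. A model of the share therefore conditions on something the intervention may move, and leaves out whatever part of a count effect comes through volume.

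For new starts there is a second gap: the hypothesis concerns patients, while the unit of the logistic model is the fill. A prescriber who stops altogether contributes no post-letter fills to that model, although that prescriber's starts have fallen to zero.

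At stake is the reported answer to two secondary questions. The trial could report no change in new starts when the number fell, or a rise when it did not rise. It could also understate a fall in high-dose prescriptions.

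**Working it through.** The plan states no figure on this point, so there is none to reproduce. All changes and baseline shares below are assumptions, and the control arm is held constant.

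**Identity.** Let H be the fills of interest and T total fills, with 0 for before and 1 for after the letter:

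H1/H0 = [(H1/T1)/(H0/T0)] × (T1/T0), that is, count ratio = share ratio × total-fills ratio.

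This holds in totals. The planned regressions work at fill or clinician level, so their coefficients would differ somewhat, but averaging shares does not put the volume term back.

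**New starts.** Suppose each new patient gives one new-start fill. If new-start fills are multiplied by a and continuing fills by b, the odds ratio is a/b whatever the baseline split.

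| New starts | Continuing fills | Count ratio a | Odds ratio a/b |
|---|---|---|---|
| −5% | −5% | 0.95 | 0.95/0.95 = 1.00 |
| −10% | −10% | 0.90 | 0.90/0.90 = 1.00 |
| unchanged | −5% | 1.00 | 1/0.95 = 1.05 |
| unchanged | −10% | 1.00 | 1/0.90 = 1.11 |
| −5% | −10% | 0.95 | 0.95/0.90 = 1.06 |
| −10% | unchanged | 0.90 | 0.90/1.00 = 0.90 |

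Check of the fifth row from 20 new and 80 continuing fills: 19 and 72 remain, total 91. The share goes from 20.0% to 19/91 = 20.9%, a ratio of 1.044, and 1.044 × 0.91 = 0.95. The number fell and the share rose. The two measures agree only in the last row.

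A larger fall in continuing fills than in starts is possible under this letter. One strategy in Section 5.1 is to "avoid prescriptions lasting greater than 3-months for" pain, which bears on continuing fills, and none of the five listed strategies names starting a patient.

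**High-dose fills**, from an assumed 20 of 100:

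| Change | After | Count ratio | Share ratio |
|---|---|---|---|
| All fills −5%, same mix | 19/95 = 20% | 0.95 | 1.00 |
| All fills −10%, same mix | 18/90 = 20% | 0.90 | 1.00 |
| 10% of high-dose fills tapered, stay in denominator | 18/100 = 18% | 0.90 | 0.90 |
| 10% tapered, then all fills −5% | 17.1/95 = 18% | 0.855 | 0.90 |
| 10% tapered, then all fills −10% | 16.2/90 = 18% | 0.81 | 0.90 |

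Wherever tapering occurs, the share still shows a reduction. In the last row a 19% fall in number appears as a 10% fall in share. A null needs unchanged mix. A reversal would need other fills to fall proportionally more than high-dose fills, whereas the letter asks prescribers to "consider slow tapers with pauses to below 50 MME per day".

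**Precision of a count.** Section 9.2 gives 65 decedents per arm and 4.5 prescribers each: 65 × 4.5 = 292.5 prescribers per arm. If prescribers' log volume change has standard deviation s (assumed 0.3 to 0.6), it adds a standard-error component of s × √(2/292.5) = 0.0827s to the log count ratio, or 0.025 to 0.050. This is before clustering. Section 9.2 also assumes an intracluster correlation of 0.2 and a coefficient of variation of 1.22. With L = 0.9/(0.9 + 0.8) = 0.529, the Taylor-type design effect is 1.70/(1 − 1.22² × 0.529 × 0.471) = 2.70. If that applied to volume changes, the component would be multiplied by √2.70 = 1.64, giving 0.041 to 0.082. For comparison, ln(0.95) = −0.051.

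**The case against.** The strongest case on the other side has five parts.

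- *The Précis promises count outcomes.* It lists total opioid prescriptions and prescriptions of at least 100 MME as outcomes to be analysed, and the first supplies the factor that the shares omit. This stands to the extent that one cannot say the plan ignores numbers. But Section 9.5 gives these outcomes no model, and neither is a count of new patients started.
- *The high-dose model is censored, with no stated unit.* Section 9.5 keeps no-fill days as the discrete part of the primary model. If the high-dose model did the same, some volume effect would reach it. This stands as an open question. It cannot help a per-fill logistic model.
- *The letter targets mix.* For high-dose fills this stands: attenuation is the expected consequence.
- *The letter may also reduce starts.* Section 2.1 counts fewer new starts as part of cautious prescribing, and Section 5.1 covers acute pain and use of the monitoring programme. Slow tapers may keep continuing patients filling. This stands against any claim that reversal is likely. It leaves intact that the model cannot separate the two movements.
- *The figures are illustrative.* They are. The 5% in Section 9.2 is a difference in mean MME, not in fills. The 292.5 may also be too high, because a shared prescriber is assigned to one decedent only and the documents do not say whether 4.5 is a de-duplicated mean.

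A reader might infer that both secondary tests are blind to any fall in numbers, or that the new-start odds ratio will point the wrong way. The documents support neither reading, for the reasons above. Nor is the primary analysis affected in this way: it retains no-fill days and would register a general fall in MME, though it tests neither of these hypotheses.

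**Conclusion.** The point holds, with different strength for the two outcomes.

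For new starts it is definite and follows from the text: a question about a number of patients is given a model conditional on fills. That model returns an odds ratio of 1.00 when starts and continuing fills fall together, and one above 1 when continuing fills fall more (1.06 for falls of 5% and 10%).

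For high-dose prescriptions the percent model leaves out the effect through total fills. This usually means attenuation, and a null only if mix is unchanged. Confidence is lower here because the unit and the handling of no-fill units are unstated.

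The actual size cannot be computed: the documents give no baseline shares and no expected changes in fills. The share remains a legitimate measure of prescribing mix. Because these are secondary outcomes and the remedy is cheap, this is an improvement that should be made; it does not undermine the trial.

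**What to change.** Keep both share analyses and label them as measures of prescribing mix. State the unit of the high-dose percent and how units with no fills enter.

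Beside them, add a difference-in-differences count model (for example negative binomial) of new patients started and of high-dose prescriptions, per randomised prescriber per period. Use equal exposure time before and after, keep prescribers with zero fills, and cluster on decedent. Fit it for the 3-month windows of Section 9.5 (post-period starting one month after the letter) and for the 12-month comparison in the Précis. The 13 months of follow-up in Section 6.1.3 would cover one month of washout plus 12. Define a new start, including its look-back period; the documents give no definition and both analyses need one.

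Draw any conclusion about *fewer* from the count, reported with its confidence interval. If no count model is added, reword the two hypotheses, the objective in Section 1.2 and the conclusions as shares of fills.

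The work is small, since the same CURES fill records serve. The cost is precision: stable volume differences between prescribers cancel in the pre-post comparison, but changes in case volume do not, so the count may be imprecise and a non-significant result must not be read as no effect. Section 9.4.2 is in the past tense and Section 9.5 in the future tense; if the share analyses have already been run, label the counts as added afterwards. Rewording alone costs nothing but gives up the question about numbers.

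Separately, the high-dose cut-offs in the Précis (at least 100 MME) and in Sections 9.4.2 and 9.5 (at least 50 or over 90 MME per day) differ and must be reconciled.

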9. STATISTICAL CONSIDERATIONS

9.1 General Design Issues

The study is a decedent-cluster randomized field experiment; clusters of prescribers within each decedent were randomly allocated to either treatment or control. This design avoided treatment contamination—clinicians prescribing to the same patient were able to share information about the intervention without diluting its effect. If two or more decedents had the same prescriber, that prescriber was assigned to one and only one of those decedents by random draw. Two factors served as random strata: 1) whether the decedent received a prescription from a clinician with a single or multiple deaths, and 2) whether opioids only, opioids in combination with benzodiazepines, or benzodiazepines only were the cause of death. The first strata is designed to form equivalent groups on prescriber risk posture. The second strata equated preference for type of scheduled drug prescribed in practice. Strata were crossed to form $2 \times 3 = 6$ randomization groups.

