9.5 Data Analyses

Descriptive and inferential statistics will be carried out in STATA (Version 14.0; Stata Corporation, College Station, TX). The *cmp* command in STATA will be used to compute a difference-in-differences estimator within a mixed-model censored linear regression.(17) The difference-in-differences estimator compares the average change over time in MME dispensed for prescribers in the intervention group, compared to the average change over time for prescribers in the control group. The natural log transformation of MME ensures normally distributed data. Censored regression has a continuous component and a discrete one. Natural log MME doses estimated over days where opioids were dispensed in the name of a prescriber represent the continuous part, and days with no opioids filled in that prescriber’s name represent the discrete part of the model. We denote estimation of the dependent variable as $\log(\overline{MME})^*$ to distinguish it from uncensored estimation. The analysis is represented by:

$$\log(\overline{MME})^*_{ijk} = \beta_1 x_{1ij} + \beta_2 x_{2ij} + \beta_3 x_{3ij} + \delta_{i(k)} \quad [1]$$

where β_1, β_2 and β_3 are fixed effects coefficients on time, x_1 , intervention, x_2 , and time by intervention interaction, x_3 , respectively. Alphabetic subscripts describe the i th prescriber, j th prescription filled and k th decedent, the nested random intercept $\delta_{i(k)}$ is normally distributed with mean zero and variance, $\sigma_{i(k)}^2$, for each i prescriber nested in (i.e., having prescribed to) decedent $k, i(k)$. With natural log transformed data, the value $100 \cdot [\exp\{\beta_3\} - 1]$ measures the percentage change in MME attributable to the intervention when data are uncensored.(18) However, when data are censored the coefficient β_3 must be adjusted to reflect the effect on the observed outcome. We will evaluate data 3 months pre-intervention and 3 months post-intervention, with

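### The new-start logistic model names no method for clustering by prescriber or decedent; fitted as ordinary logistic regression, its false-positive rate can exceed 5%

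*Combined protocol and SAP*

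**What the plan says.** Section 1.2 makes the number of new starts a secondary objective. Section 9.5 gives the analysis: "Chance of a fill being a “new start” will be evaluated using logistic regression". Section 9.4.2 has the same sentence in the past tense ("were evaluated using logistic regression" where Section 9.5 has "will be evaluated using logistic regression"). Section 9.5 adds: "These analyses will also be conducted within a difference-in-differences framework". The unit of analysis is therefore the fill.

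Allocation is at a higher level. Under Section 9.1, "clusters of prescribers within each decedent were randomly allocated to either treatment or control". Section 9.2 sizes the trial with a mean of 4.5 prescribers per decedent, a coefficient of variation of 1.22 and an intracluster correlation of 0.2.

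For the primary outcome, Section 9.5 does name a multilevel model: the *cmp* command "will be used to compute a difference-in-differences estimator within a mixed-model censored linear regression". Equation [1] has one random intercept, for "prescriber nested in (i.e., having prescribed to) decedent" k, and is written for log MME only. For new starts, neither section names a random effect, a GEE or a cluster-robust variance, or says whether that intercept carries over.

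**The concern.** Fills are nested in prescribers, and prescribers in the decedents that were randomised. An ordinary logistic regression computes its standard error as if every fill were independent. If prescribers drift in volume or in their own new-start rate, fills from one prescriber move together, and the effective information is less than the number of fills suggests. A letter with no effect could then be declared effective on a stated secondary objective.

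A second issue concerns the estimate. A pooled fill-level odds ratio can move because the letter changes which prescribers contribute fills, even if no prescriber changes the share of fills that are new starts. A clustered variance does not remove that shift. The plan does not say whether it counts as effect.

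**Working it through.** **Plan's own figure.** There is none for this outcome. The 65 decedents per arm in Section 9.2 refers to MME. It cannot be reproduced because the 5% difference is relative and no baseline mean is given. Only the cluster structure is taken from it.

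**Inputs from the documents.** 65 decedents per arm; mean cluster size 4.5, CV 1.22; two-sided 5% test; intracluster correlation 0.2, with 0.05 to 0.15 given as usual.

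**Inputs assumed.**
- Mean fills per prescriber per period: 20, 60 or 200, exponentially distributed between prescribers.
- New-start chance at the median prescriber: 1/(1 + e^1.5) = 18%.
- Between-prescriber logit SD: 0.907 or 0.416. With ICC = s²/(s² + π²/3), these are 0.823/(0.823 + 3.290) = 0.20 and 0.173/(0.173 + 3.290) = 0.05.
- SD of log volume change: 0 or 0.3.
- SD of prescribers' own log-odds change: 0 or 0.3.

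**Tests compared under no letter effect.**
- *Ordinary*: the four-cell log odds ratio for time by arm, with variance Σ 1/(N p(1 − p)) over the cells.
- *Prescriber-conditioned*: a Mantel-Haenszel contrast stratified by prescriber, standing in for a prescriber intercept.
- *Decedent-robust*: the ordinary estimate, with its linearised contributions summed by decedent, squared, added and multiplied by 130/129.

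False-positive rates at 20 / 60 / 200 fills (3,000 replicates each; simulation error near 5% is √(0.05 × 0.95/3000) = 0.4 points):

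| Logit SD | Volume SD | Change SD | Ordinary | Prescriber-conditioned | Decedent-robust |
|---|---|---|---|---|---|
| 0.907 | 0 | 0 | 4.6 / 5.3 / 5.0% | 4.9 / 5.5 / 4.8% | 5.4 / 6.5 / 6.0% |
| 0.907 | 0.3 | 0 | 6.8 / 13.1 / 26.0% | 4.7 / 5.8 / 4.8% | 5.6 / 6.2 / 6.4% |
| 0.907 | 0.3 | 0.3 | 11.1 / 22.3 / 43.2% | 8.7 / 16.3 / 33.5% | 6.0 / 6.3 / 6.2% |
| 0.416 | 0.3 | 0 | 5.5 / 6.6 / 10.3% | 5.1 / 5.3 / 4.5% | 5.8 / 6.0 / 5.8% |

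The first row stays at 5% because the tested term is a before-after interaction. A prescriber whose rate and share of fills are stable enters both periods with equal weight and opposite sign, and cancels. The third row shows why a prescriber intercept alone may not be enough: it removes level, not variation in change.

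**More skewed volumes.** With a median of 60 fills, log-SD 1.2 (mean 60 × e^0.72 ≈ 123) and logit SD 1.0, ordinary logistic regression gives:
- 4.9% with no variation
- 19.3% with volume SD 0.2
- 32.5% with volume SD 0.3
- 21.7% with change SD 0.2 alone
- 42.0% with volume SD 0.3 and change SD 0.2

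A rate of 19.3% corresponds to a true-to-naive standard error ratio of 1.96/1.30 = 1.5, and 42.0% to 1.96/0.806 = 2.4. In comparable scenarios, a prescriber-stratified contrast with a decedent jackknife gave 4.9% to 5.5%.

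**Sensitivity at volume SD 0.3, no change variation** (800 replicates): 60 fills without skew, 10%; median 20 with skew, 16%; the same with logit SD 0.5, 9%; median 20, no skew, logit SD 0.5, 5%.

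**Composition.** Suppose 30% of fills come from prescribers with 60% new starts and 70% from prescribers with 10%. The pooled share is 0.3 × 0.6 + 0.7 × 0.1 = 0.25. If the second group cuts fills by 10%, it becomes 0.243/0.93 = 0.2613, an odds ratio of 1.06. With a 20% cut it is 0.236/0.86 = 0.2744, an odds ratio of about 1.13. No prescriber's own rate has changed. The split is illustrative.

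**The case against.** **A reader might infer that the plan specifies a one-level model that treats fills as independent.** It does not say so. The only difference-in-differences framework that Section 9.5 defines sits inside a mixed model with a prescriber-in-decedent intercept, and carrying that intercept over is a plausible reading. This stands against any claim that clustering is ignored by design. It does not close the gap, because that section defines the estimator as a comparison of average changes, separable from the mixed model, and the intercept alone does not hold 5% when prescribers' changes vary.

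**A reader might infer that the standard error is always too small.** The first row of the table contradicts that. Inflation needs shifting volumes or prescriber-specific change, and it grows with fills per prescriber. None of these inputs is in the documents, and some plausible combinations leave the error near 5%. This stands, and is why a range is given. Stable volume is still a weak assumption here: the Précis lists fewer opioid prescriptions as an expected outcome.

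**A reader might infer that the odds ratio is biased.** Under random volume change with no letter effect, the mean log odds ratio stayed within 0.006 of zero. The estimate shifts only if volume change differs by arm and is related to new-start rate. Since the stated target is the chance that a fill is a new start, a letter-induced change in the mix of fills may belong to the effect. That is partly a choice of estimand, which the plan should make explicit.

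Finally, this is a secondary outcome with no sample size or error rate of its own. One statement on variance for all models could settle it, provided that it is not limited to equation [1].

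**Conclusion.** The point holds as an unspecified clustering method with a conditional consequence. For the new-start model, the plan names logistic regression on fills and nothing that reflects randomisation by decedent. Over the assumed ranges, ordinary logistic regression has a false-positive rate of about 5% when volumes and prescriber rates are stable. When they vary it is roughly 10% to 40% in most settings, with some combinations of few fills or little spread staying near 5% to 7%. A prescriber intercept alone gives about 9% to 34% when prescribers' changes have SD 0.3. Decedent-level variance gives about 5% to 7% throughout.

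Confidence is high about the omission and lower about the size. The simulations used prescriber-level variation only, with no change shared within a decedent, so they do not show what such sharing would add. The plan should be amended, but the primary analysis is not affected by this point.

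**What to change.** In Sections 9.4.2 and 9.5:

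1. State that the new-start difference-in-differences logistic model takes its standard error by decedent, by cluster-robust or delete-one-decedent jackknife variance with a t reference. A re-randomisation test that redraws decedent order within each of the six lists is an alternative.
2. State whether the target is the pooled fill-level odds ratio or a within-prescriber contrast.
3. Add a prescriber-conditioned version as a sensitivity analysis, also with decedent-level variance, so that a shift in which prescribers contribute fills can be seen.

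This takes a few sentences and a different command option, and needs no new data. The downside is wider confidence intervals for this secondary outcome.
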